1. OBJECTIVES

1.1 Study Design

This is a Phase II trial of nivolumab and ipilimumab in leptomeningeal carcinomatosis.

1.2 Primary Objectives

To estimate the overall survival of the combination of nivolumab and ipilimumab in leptomeningeal metastases

1.3 Secondary Objectives

1. To describe the toxicity of nivolumab and ipilimumab in brain and leptomeningeal metastases.
2. To estimate the central nervous system response rate (parenchymal brain metastases) of nivolumab and ipilimumab in patients with leptomeningeal disease
3. To estimate the systemic response rate of nivolumab and ipilimumab in patients with brain metastases
4. To estimate leptomeningeal disease response of nivolumab and ipilimumab in patients with leptomeningeal metastases.
5. To estimate the systemic progression free-survival of patients receiving nivolumab and ipilimumab.
6. To estimate the intracranial progression free-survival of patients receiving nivolumab and ipilimumab.

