The unique immune-based mechanism of action is also reflected in the safety profile. The most common treatment-related AEs are inflammatory in nature, consistent with the mechanism of action of the drug and generally medically manageable with topical and/or systemic immunosuppressants. Such immunological safety events are described as immune-related adverse events (irAEs) or immune-mediated adverse reactions (imARs). The irAEs are described as AEs of unknown etiology, which were consistent with an immune phenomenon and were considered causally related to drug exposure by investigators. The irAEs primarily involve the GI tract and skin. Immune-related AEs in the liver were also observed, particularly in subjects receiving 10 mg/kg. Endocrinopathy and neuropathy were important irAEs observed less frequently. The imARs were adjudicated in a blinded fashion based on sponsor-physician data review to exclude noninflammatory etiologies, such as infection or tumor progression, and to consider available evidence of inflammation, such as tumor biopsies or responsiveness to steroids, in an effort to determine whether specific AEs or abnormal hepatic laboratory values were likely to be immune mediated and associated with ipilimumab treatment. The early diagnosis of inflammatory events is important to initiate therapy and minimize complications. Inflammatory events are generally manageable using symptomatic or immuno-suppressive therapy as recommended through detailed diagnosis and management guidelines.

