- 3.1.7. Women of childbearing potential must have a negative serum or urine pregnancy test (minimum sensitivity 25 IU/L or equivalent units of HCG) within 72 hours prior to the start of nivolumab.
- 3.1.8. Women must not be breastfeeding.
- 3.1.9. Men who are sexually active with WOCBP must use any contraceptive method with a failure rate of less than 1% per year. Men receiving nivolumab and who are sexually active with WOCBP will be instructed to adhere to contraception for a period of 31 weeks after the last dose of investigational product. Women who are not of childbearing

potential, ie, who are postmenopausal or surgically sterile as well as azoospermic men do not require contraception

- 3.1.7 Ability to understand and the willingness to sign a written informed consent document.
- 3.1.8 Stable dose of dexamethasone 2 mg or less for 7 days prior to initiation of treatment
- 3.1.9 Carcinomatous meningitis, as defined by positive cytology or biopsy. If CSF cytology is negative, but imaging is consistent with carcinomatous meningitis, patient is eligible.

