5. TREATMENT PLAN

5.1 Treatment Regimen by histology:

For melanoma: patients will be treated with the combination regimen of nivolumab 1 mg/kg combined with ipilimumab 3mg/kg Q3W (4 doses), followed by nivolumab monotherapy (480 mg Q4W) until progression or unacceptable toxicity.

For nonsmall cell lung cancer and head and neck cancer: patients will be treated with nivolumab 3mg/kg Q2W + ipilimumab 1mg/kg Q6W

For small cell lung cancer, breast cancer, and bladder cancer: patients will be treated with nivolumab 1mg/kg + ipilimumab 3mg/kg Q3W x 4 doses, followed by nivolumab 240 mg Q2W

For renal cell carcinoma and other solid tumors (not listed above): patients will be treated with nivolumab 3mg/kg + ipilimumab 1mg/kg Q3W x 4 doses, followed by nivolumab 480 mg Q4W

Each treatment cycle will be 6 weeks, with the exception of the nivolumab maintenance monotherapy phase in melanoma, renal cell carcinoma and other solid tumors, when each cycle will be 8 weeks. Treatment will be administered on an outpatient basis. Reported adverse events and potential risks are described in Section 7. Appropriate dose modifications are described in Section 6. No investigational or commercial agents or therapies other than those described below may be administered with the intent to treat the participant's malignancy.

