13. STATISTICAL CONSIDERATIONS

This is a single arm phase II trial to investigate the therapeutic effect of ipilimumab and nivolumab in leptomeningeal carcinomatosis.

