13.2 Sample Size, Accrual Rate and Study Duration

Accrual of up to 20 patients may be required to achieve 18 evaluable patients.

The primary endpoint is the rate of overall survival at 3 months (OS3). Any patient whose vital status at 3 months cannot be determined will be counted as having died. A Simon two-stage design will be used to compare a null hypothesis OS3 of 18% against an alternative of 43%. Nine patients will be enrolled in the first stage. If 0 or 1 patients are alive at 3 months, the trial will be stopped early. If 2 or more patients are alive at 3 months, we will enroll an additional 9 patients. If at least 6 patients among the total of 18 patients are alive at 3 months, then the treatment would be promising in the cohort. This design has a type-I error of 8% (target 10%) and power of 86% (target 85%). If the null hypothesis is true, then the probability is 0.50 of stopping at the end of the first stage.

In addition, we will assess for the primary outcome of any histologic, molecular subtype (e.g., ER/PR-positive, HER2-positive breast cancer, EGFR mutant lung cancer) with 6 patients

enrolled for that particular subtype. If no patient within a particular histologic subtype has achieved the primary outcome, then patients with that histology will no longer be eligible to enroll in the trial. Under the alternative hypothesis (i.e., OS3 = 43%), the probability is 0.03 of observing no patients with OS3 among 6 patients.

The accrual rate is based on our institutional patient volume of 3-4 patients per month with leptomeningeal carcinomatosis seen in our multidisciplinary brain metastasis clinic. We estimate that 1-2 patients per month will be eligible for this protocol. Therefore, 20 patients will be accrued within 10-20 months. Based on six months of follow-up (median survival of patients is approximately 2-4 months), total study duration will be 24 months.

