13.6 Analysis of Secondary Endpoints

Safety and Tolerability: All adverse events recorded during the trial will be summarized for all patients having received one or more doses of ipilimumab and nivolumab. The data for each cohort will be summarized separately, although safety data may be combined, if appropriate. The proportions of patients with grade-3 or higher hematologic toxicities or grade-3 or higher neurologic toxicities will be presented with 90% exact binomial confidence intervals. The incidence of events that are new or worsening from the time of first dose of treatment will be summarized according to system organ class and/or preferred term, severity (based on CTCAE grade), type of adverse event, and relation to study treatment. Deaths reportable as SAEs and non-fatal serious adverse events will be listed by patient and tabulated by primary system organ class, and type of adverse event.

Intracranial/Extracranial Response: The proportion of patients with intracranial response of intraparenchymal brain metastases (CR or PR by RANO) will be presented with a two-sided, 90% exact binomial confidence interval. For a sample of 18 patients, the confidence interval will have maximum width of 0.42. Extracranial response rates (CR or PR) according to RECIST and irRC will be summarized. Rates will be accompanied by two-sided 90% exact binomial

confidence intervals. Cases where RECIST and irRC responses do not agree will be documented.

Leptomeningeal Disease Response: The proportion of patients with leptomeningeal disease response (CR or PR) will be presented with a two-sided, 90% exact binomial confidence interval. For a sample of 18 patients, the confidence interval will have maximum width of 0.42.

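### Secondary objective 3 names patients with brain metastases in a trial that enrols leptomeningeal disease, and Section 13.6 reports safety and PFS by a cohort that is never defined, although three ipilimumab schedules are in use.

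*Combined protocol and SAP*

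**What the plan says.** **Population.** Section 1.3 gives objective 3 as "To estimate the systemic response rate of nivolumab and ipilimumab in patients with brain metastases" and objective 1 as "To describe the toxicity of nivolumab and ipilimumab in brain and leptomeningeal metastases". Objectives 2 and 4 are set in patients with leptomeningeal disease. Section 3.1 requires "Carcinomatous meningitis, as defined by positive cytology or biopsy", or imaging consistent with it when cytology is negative; no entry criterion asks for brain metastases. Endpoint 3 in Section 13.1 is extracranial response by RECIST and irRC, with no restriction to a subgroup, and Section 13.6 analyses it the same way.

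**Grouping.** Section 13 opens: "This is a single arm phase II trial to investigate the therapeutic effect of ipilimumab and nivolumab in leptomeningeal carcinomatosis". Section 13.2 uses the singular, saying that with enough survivors "then the treatment would be promising in the cohort", and Section 13.3 (stratification) is marked not applicable. Yet Section 13.6 says of safety: "The data for each cohort will be summarized separately, although safety data may be combined, if appropriate". For extracranial and intracranial PFS it asks for each cohort separately and mentions no combining.

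**Treatment.** Section 5.1 assigns treatment by histology. Melanoma, small cell lung, breast and bladder cancer get nivolumab 1 mg/kg with ipilimumab 3 mg/kg every 3 weeks for 4 doses. Renal cell carcinoma and other solid tumors get nivolumab 3 mg/kg with ipilimumab 1 mg/kg on that schedule. For non-small cell lung and head and neck cancer, "patients will be treated with nivolumab 3mg/kg Q2W + ipilimumab 1mg/kg Q6W".

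**The concern.** An objective should name the population that its analysis uses. Objective 3 names one that the trial neither requires nor selects. Section 2.1 reports only an association, in melanoma, between parenchymal brain metastases and leptomeningeal disease, so the two groups cannot be taken as the same.

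The cohort instruction cannot be carried out as written. An analyst must decide what a cohort is, and whether combining safety data is appropriate, with no stated criterion and possibly after seeing the data. This matters most for toxicity, because patients in the single arm do not all receive the same treatment. A combined proportion of patients with grade 3 or higher hematologic or neurologic toxicity would be an average over regimens, weighted by the histologies that happened to enrol.

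**Working it through.** **1. The plan's own precision figure.** Section 13.6 states a maximum width of 0.42 for a 90% exact interval with 18 patients (given for intracranial and leptomeningeal response; none is given for extracranial response or toxicity). The Clopper-Pearson limits for x events in n are the 5% quantile of Beta(x, n − x + 1) and the 95% quantile of Beta(x + 1, n − x). At n = 18 the widest interval is at x = 9, with width 0.418. The stated figure reproduces.

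**2. Populations side by side.**

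| Place | Population for systemic response |
|---|---|
| 1.3, objective 3 | patients with brain metastases |
| 3.1, entry | leptomeningeal disease; brain metastases not required |
| 13.1, endpoint 3 | no restriction |
| 13.6, analysis | no restriction |

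Only the objective differs. Following Section 13.6, the number excluded for lack of brain metastases is zero.

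**3. Planned dose through week 12** (Section 5.1; dosing weeks from the Section 10 calendars).

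| Induction regimen | Ipilimumab, mg/kg | Nivolumab, mg/kg |
|---|---|---|
| Ipilimumab 3 mg/kg Q3W, 4 doses | 4 × 3 = 12 | 4 × 1 = 4 |
| Ipilimumab 1 mg/kg Q3W, 4 doses | 4 × 1 = 4 | 4 × 3 = 12 |
| Ipilimumab 1 mg/kg Q6W (weeks 1 and 7) | 2 × 1 = 2 | 6 × 3 = 18 |

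The ipilimumab ratio between the extreme regimens is 12/2 = 6; the other pairs give 12/4 = 3 and 4/2 = 2. Q6W dosing continues beyond week 12, so the extreme ratio falls to 12/3 = 4 at week 18, 12/4 = 3 at week 24 and 12/8 = 1.5 at week 48. Nivolumab is ordered in reverse.

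**4. Effect of pooling.** Take two regimens with event rates a and b and a share s of patients on the first. The expected pooled proportion is s·a + (1 − s)·b. Moving from 6 of 18 to 12 of 18 patients on the first regimen changes it by (12/18 − 6/18)·(a − b), one third of the difference in rates. The documents give no grade 3 or higher hematologic or neurologic rates by regimen, so a − b is unknown and may be small.

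**5. Precision by regimen.** The maximum 90% exact width is 0.58 at n = 9, 0.69 at n = 6 and 0.80 at n = 4, against 0.42 for 18 pooled.

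**6. A conflict that affects the grouping.** Section 5.1 puts other solid tumors with renal cell carcinoma (ipilimumab 1 mg/kg, nivolumab 3 mg/kg). Footnotes A and B of the induction calendar in Section 10 put them with melanoma (ipilimumab 3 mg/kg, nivolumab 1 mg/kg). The regimen of these patients cannot be read from the protocol until the two are reconciled.

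**The case against.** The strongest reply is that these are wording slips with little consequence. Several parts of it stand.

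- A reader might infer that patients without brain metastases would be dropped from the systemic response rate. Sections 13.1 and 13.6 govern the analysis and carry no such limit.
- A reader might infer that objective 1 is also set in the wrong patients. It covers brain and leptomeningeal metastases, so the enrolled group is included; it is only loosely worded.
- A reader might infer that a case-mix average is the planned toxicity estimate. Section 13.6 makes separate summaries the default and combining optional. If cohort meant regimen, the text would already deliver the safety display asked for here.
- A reader might call the regimens sixfold different in exposure. Six is a ratio of planned ipilimumab dose, between the extreme regimens, to week 12 only, with nivolumab reversed.
- Evidence in the protocol that toxicity differs between these ipilimumab doses is thin. Section 2.2.1 says "Immune-related AEs in the liver were also observed, particularly in subjects receiving 10 mg/kg", a dose not used here. The animal data escalate both drugs together. Initial cohorts 1 to 3 of the combination study in Section 2.2.3 all received ipilimumab 3 mg/kg.

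What does not stand is that cohort can be left to interpretation. Regimen is one reading. Histology is another, since Section 13.2 has a rule closing a histology after no successes among 6 patients. The whole single arm is a third. They give different tables, and the plan chooses none.

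**Conclusion.** The point holds as a correction to the secondary objectives and the safety reporting. Objective 3 names a population that differs from the enrolled one and from its own endpoint and analysis; the error lies in the objective and changes no planned denominator. Cohort is undefined in Section 13.6, so the safety and PFS displays are not fixed in advance. If safety data are combined, the toxicity proportions depend on histology mix to the extent that rates differ between regimens. That the regimens differ is certain from Section 5.1 (12, 4 or 2 mg/kg of planned ipilimumab through week 12). How far their toxicity differs is not known from the documents, so no size is claimed for the shift. The two-stage decision on 3-month survival does not use any of this text.

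**What to change.** - **Objective 3:** set it in patients with leptomeningeal metastases who have extracranial disease evaluable at baseline, and state that this denominator may be below 18.
- **Objective 1:** tidy to patients with leptomeningeal metastases.
- **Section 13.6, safety:** replace the reference to each cohort by each induction regimen actually received. Give counts and 90% exact intervals per regimen beside the pooled figure, as description only, with no comparison between regimens.
- **Section 13.6, extracranial and intracranial PFS:** delete the cohort sentence, or define cohort in the same way.
- **Before grouping:** reconcile Section 5.1 with footnotes A and B of the Section 10 induction calendar on other solid tumors.

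The cost is wording in Sections 1.3 and 13.6 and one extra table, with no added patients or procedures. The downside is imprecision: with small regimen groups the intervals will be too wide to separate one regimen from another and should be presented as such.

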1.4 Correlative Objectives

1. To determine molecular biomarkers of response using next generation sequencing techniques.

2. BACKGROUND

2.1 Study Disease(s)

Approximately 5-8% of patients with cancer develop leptomeningeal carcinomatosis¹. While virtually any malignancy can metastasize to the leptomeninges, this most commonly occurs with lung cancer, breast cancer and melanoma. Approximately 5-7% of patients with melanoma develop leptomeningeal carcinomatosis and there seems to be an association with the presence of parenchymal brain metastases and the development of leptomeningeal carcinomatosis². As patients with cancer survive longer and diagnostic imaging techniques improve, leptomeningeal carcinomatosis is being diagnosed more frequently. Patients typically present with signs of increased intracranial pressure, cranial nerve palsies, seizures, stroke-like symptoms,

encephalopathy, radiculopathies and cauda equina syndrome¹. The median survival of patients with leptomeningeal metastases without treatment is approximately 4-6 weeks. Death usually results from rapid progressive neurologic deterioration. Treatment involves radiation to symptomatic sites of the neuraxis and to sites of bulk disease seen on imaging studies. Systemically administered chemotherapy has limited access to the CSF due to the blood-brain barrier. Intrathecal chemotherapy is designed to treat tumor cells floating in the cerebrospinal fluid (CSF), thereby preventing the development of new symptomatic sites of disease; however treatment-related toxicities of intrathecal chemotherapy are common, and include chemical meningitis, seizures and severe headaches³. Radiotherapy and intrathecal chemotherapy provide local control and may extend median survival of patients with leptomeningeal carcinomatosis to 3-6 months^{3,4}. Novel therapies are needed to improve outcomes in patients with leptomeningeal carcinomatosis.

2.2 IND Agents

2.2.1 Ipilimumab

Ipilimumab (BMS-734016, MDX010, MDX-CTLA4) is a fully human monoclonal immunoglobulin (Ig) G1κ specific for human cytotoxic T lymphocyte antigen 4 (CTLA-4, CD152), which is expressed on a subset of activated T cells. CTLA-4 is a negative regulator of T-cell activity. Ipilimumab is a monoclonal antibody that binds to CTLA-4 and blocks the interaction of CTLA-4 with its ligands, CD80/CD86. Blockade of CTLA-4 has been shown to augment T-cell activation and proliferation, including the activation and proliferation of tumor infiltrating T-effector cells. Inhibition of CTLA-4 signaling can also reduce T-regulatory cell function, which may contribute to a general increase in T-cell responsiveness, including the anti-tumor response. Yervoy™ (ipilimumab) has been approved for use in over 47 countries including the United States (US, Mar-2011), the European Union (EU, Jul-2011), and Australia (Jul-2011).

Nonclinical Studies

Ipilimumab has specificity and a high affinity for human CTLA-4. The calculated dissociation constant value from an average of several studies was 5.25 nM. Binding of ipilimumab to purified, recombinant human CTLA-4 antigen was also demonstrated by enzyme-linked immunosorbent assay with half-maximal binding at 15 ng/mL, whereas saturation was observed at approximately 0.1 μg/mL. No cross-reactivity was observed against human CD28. Ipilimumab completely blocked binding of B7.1 and B7.2 to human CTLA-4 at concentrations higher than 6 μg/mL and 1 μg/mL, respectively.

Effects in Humans

Bristol-Myers Squibb (BMS) and Medarex, Inc. (MDX, acquired by BMS in Sep-2009) have co-sponsored an extensive clinical development program for ipilimumab, encompassing more than 19,500 subjects (total number of subjects enrolled in ipilimumab studies) in several cancer types in completed and ongoing studies, as well as a compassionate use program. The focus of the clinical program is in melanoma, prostate cancer, and lung cancer, with advanced melanoma being the most comprehensively studied indication. Ipilimumab is being investigated both as monotherapy and in combination with other modalities such as chemotherapy, radiation therapy, and other immunotherapies. Phase 3 programs are ongoing in melanoma, prostate cancer, and

lung cancer. In melanoma, 2 completed Phase 3 studies (MDX010-20 and CA184024) have demonstrated a clinically meaningful and statistically significant survival benefit in pretreated advanced melanoma and previously untreated advanced melanoma, respectively. The safety profile of ipilimumab is generally consistent across these trials with a) the majority adverse events (AEs) being inflammatory in nature consistent with the proposed mechanism of action of ipilimumab, b) the same types of such immune-mediated events in the gastrointestinal (GI) tract, skin, liver, and endocrine system being reported, and c) most of these events being manageable with immune suppressive therapies.

In melanoma, 2 BMS-sponsored Phase 3 studies are ongoing in subjects with high-risk Stage III melanoma (CA184029, with adjuvant immunotherapy) and pretreated and treatment-naïve advanced melanoma (CA184169, 3 mg/kg versus 10 mg/kg ipilimumab). The completed Phase 3 study CA184043 evaluated ipilimumab in subjects with metastatic castration-resistant prostate cancer (mCRPC) who had progressed during or following docetaxel. Eligible subjects were randomized to a single dose of bone-directed radiotherapy (RT), followed by either ipilimumab 10 mg/kg or placebo (799 randomized: 399 ipilimumab, 400 placebo). This study did not meet its primary endpoint of overall survival (OS). The hazard ratio (HR) of 0.85 (95% confidence interval [CI]: 0.72 to 1.00) for survival favored ipilimumab but did not reach statistical significance with a P-value of 0.053. Planned sensitivity analyses favored ipilimumab, where the greatest benefit appeared to be in subgroups defined by good prognostic features and low burden of disease. Additional evidence of ipilimumab activity observed in the study included a reduced risk of disease progression relative to placebo (HR = 0.70) and superior clinical outcomes compared to placebo in tumor regression and declines in prostate specific antigen (PSA). The safety profile in this study was consistent with the previously defined AE profile at the same dose.

A second Phase 3 study CA184095 evaluating ipilimumab 10 mg/kg versus placebo in men with asymptomatic or minimally symptomatic, chemotherapy-naïve mCRPC with no visceral metastases has completed enrollment and is currently in follow-up. In addition, a completed large Phase 2 study (CA184041) has investigated the addition of ipilimumab to carboplatin and paclitaxel using 2 different schedules (concurrent and phased) in subjects with non-small cell lung cancer (NSCLC) or small cell lung cancer (SCLC, a secondary endpoint). Ipilimumab, given in combination with paclitaxel/carboplatin in a phased schedule improved irPFS compared to the control treatment, but no improvement was seen when ipilimumab was given in a concurrent schedule. Phased ipilimumab also improved PFS according to mWHO criteria and showed a trend for improved OS. The efficacy and safety of ipilimumab in a phased schedule with carboplatin/paclitaxel is also being investigated in an ongoing Phase 3 study in subjects with advanced squamous NSCLC (CA184104). The efficacy and safety of ipilimumab in a phased schedule with etoposide/platinum in subjects with extensive stage disease SCLC is being investigated in an ongoing Phase 3 study (CA184156).

The unique immune-based mechanism of action is reflected in the clinical patterns of anti-cancer activity in some patients. Ipilimumab induces an immunologic response, and measurable clinical effects emerge after the immunological effects. Tumor infiltration with lymphocytes and the associated inflammation (documented by biopsy in some subjects) is likely the cornerstone of the effect of ipilimumab and can manifest in various patterns of clinical activity leading to tumor

control. In some cases, inflammation may not be noted by radiological examination and objective response is observed with the first tumor assessment in a manner seen in patients receiving other types of anti-cancer treatments. In other cases, response may be preceded by an apparent increase in initial tumor volume and/or the appearance of new lesions, which may be mistaken for tumor progression on radiological evaluations. Therefore, in patients who are not experiencing rapid clinical deterioration, confirmation of progression is recommended, at the investigator's discretion, to better understand the prognosis as well as to avoid unnecessarily initiating potentially toxic alternative therapies in subjects who might be benefiting from treatment. Immune-related response criteria were developed based on these observations to systematically categorize novel patterns of clinical activity and are currently being prospectively evaluated in clinical studies. In metastatic diseases, stabilization is more common than response, and in some instances is associated with a slow, steady decline in tumor burden over many months, sometimes improving to partial and/or complete responses. Thus, the immune-based mechanism of action of ipilimumab results in durable disease control, sometimes with novel patterns of response, which contribute to its unique improvement in OS.

The unique immune-based mechanism of action is also reflected in the safety profile. The most common treatment-related AEs are inflammatory in nature, consistent with the mechanism of action of the drug and generally medically manageable with topical and/or systemic immunosuppressants. Such immunological safety events are described as immune-related adverse events (irAEs) or immune-mediated adverse reactions (imARs). The irAEs are described as AEs of unknown etiology, which were consistent with an immune phenomenon and were considered causally related to drug exposure by investigators. The irAEs primarily involve the GI tract and skin. Immune-related AEs in the liver were also observed, particularly in subjects receiving 10 mg/kg. Endocrinopathy and neuropathy were important irAEs observed less frequently. The imARs were adjudicated in a blinded fashion based on sponsor-physician data review to exclude noninflammatory etiologies, such as infection or tumor progression, and to consider available evidence of inflammation, such as tumor biopsies or responsiveness to steroids, in an effort to determine whether specific AEs or abnormal hepatic laboratory values were likely to be immune mediated and associated with ipilimumab treatment. The early diagnosis of inflammatory events is important to initiate therapy and minimize complications. Inflammatory events are generally manageable using symptomatic or immuno-suppressive therapy as recommended through detailed diagnosis and management guidelines.

A program-wide independent Data Monitoring Committee (DMC) reviews data from the ipilimumab studies, allowing for an ongoing safety and benefit/risk assessment in subjects receiving ipilimumab. The DMC charter includes explicit stopping rules for some studies, allowing the DMC to recommend discontinuing further treatment across the ipilimumab program, if necessary. In summary, ipilimumab offers clinically meaningful and statistically significant survival benefit to patients with pretreated advanced melanoma (as 3 mg/kg monotherapy compared to the melanoma peptide vaccine gp100) and previously untreated advanced melanoma (at 10 mg/kg in combination with dacarbazine [DTIC] compared to DTIC alone), and evidence of clinical activity in randomized studies in other tumor types. These findings, together with evidence of a safety profile that is manageable with careful monitoring and appropriate intervention for treatment of immune-related toxicities, suggest an acceptable benefit to risk ratio.

